To: CTEP Protocol and Information Office
From: [name].
Date: March 25, 2025
Re: Response to Disapproval of Amendment #8 of Protocol #10330: “A Phase 2 Study of Belinostat and SGI-110 (Guadecitabine) or ASTX727 for the Treatment of Unresectable and Metastatic Conventional Chondrosarcoma”

SUMMARY OF CHANGES – Protocol

I. Comments Requiring a Response– Administrative & Editorial Issues:

#	Section	Comments
1.	ICD Risks	
Please add ASTX727 risk list (CAEPR version 2.2, December 19, 2024), as attached.
 
PI Response: Risks updated in applicable consent. ASTX727 risks not described in SGI-110 consent.

II. Recommendations:

#	Section	Comments
2.	8.1.4.1	
Agent Ordering and Agent Accountability
 
Update the second paragraph to:
 
Submit agent requests through the PMB AURORA application. Access to AURORA requires the establishment of credentials necessary to access secure NCI Clinical Oncology Research Enterprise (CORE) systems, maintenance of an “active” account status, a “current” password, and active person registration status. For questions about drug orders, transfers, returns, or accountability, call or email PMB any time or use the dialog function in AURORA to communicate with PMB staff. Refer to the PMB’s website for specific policies and guidelines related to agent management.
 
PI Response: Updated

3.	8.1.4.2	
Agent Inventory Records
 
In the first paragraph, replace “careful record” with “complete accountability”.
 
Add the following as a second paragraph:
 
Product Quality Complaint (PQC): A product quality complaint is defined as any suspicion of a product defect related to a potential quality issue during manufacturing, packaging, release testing, stability monitoring, dose preparation,

#	Section	Comments
		
storage or distribution of the product, or delivery system. Not all PQCs involve a study subject. Lot or batch numbers are of high significance and need to be provided where and when possible. PQC must be reported to the PMB as soon as the PQC is identified. Report PQC to PMB at [contact] or by using the dialog function in AURORA to communicate with PMB staff.
 
PI Response: Updated and Added

4.	8.1.5	
Investigator Brochure
 
Update the entire paragraph to:
 
The current versions of the IBs for the agents will be accessible to site investigators and research staff through the PMB AURORA application. Access to AURORA requires the establishment of credentials necessary to access secure NCI Clinical Oncology Research Enterprise (CORE) systems, maintenance of an “active” account status, a “current” password and active person registration status. Questions about IB access may be directed to the PMB IB Coordinator via email.
 
PI Response: Updated

5.	8.1.6	
Useful Links and Contacts
 
Change “PMB Online Agent Order Processing (OAOP) application:” to “PMB Agent Inventory Management System (AURORA) application: https://ctepcore.nci.nih.gov/aurora/login”.
 
PI Response: Updated

6.	8.1.4	
Insert the following as a new subsection:
 
Material Safety Data Sheets
 
The current versions of the material safety data sheets (MSDS or SDS) for PMB-distributed agents will be accessible to site investigators and research staff through the PMB AURORA application. Questions about MSDS access may be directed to the PMB at [contact] or by using the dialog function in AURORA to communicate with PMB staff.
 
PI Response: Added as section 8.1.4.2

7.	8.1.4	
Insert the following as a new subsection:
 
Agent Shortages
 
Specific guidance on how to address agent shortages for patients already enrolled on a clinical study as well as how to manage potential enrollment of new patients is provided at https://ctep.cancer.gov/branches/pmb/drug_shortages.htm.
 
Treatment plan modifications being made to avoid immediate hazard to patients is

#	Section	Comments
		
permissible under the Department of Health and Human Services (HHS) regulations at 45 CFR 46.103(b)(4)(iii). In accordance with HHS regulations, local investigators must promptly inform the IRB of record of this unanticipated problem and the management plan for the trial.
 
PI Response: Added as section 8.1.4.3

III. Protocol changes in response to the Request for Rapid Protocol Amendment dated 02/25/25:

#	Section	Comments
1.	Header	Updated version date
2.	Title page	
 • Updated version date and added Amendment #8 to list of versions • Updated local protocol number • Updated ClinicalTrials.gov Identifier
3.	10.3.3 Expedited Reporting Guidelines	
Specific Protocol Revisions to Address Risk Mitigation Plan
 
 • The updated AE Reporting Table
4.	10.1.1.2 CAEPR for ASTX727	
Revision of the Protocol CAEPR
 
 • The SPEER grades have been updated. • Added New Risk: 
 • Also Reported on ASTX727 Trials But With Insufficient Evidence for Attribution: Confusion; Dehydration; Hypokalemia; Intracranial hemorrhage • Increase in Risk Attribution: 
 • Changed to Less Likely from Also Reported on ASTX727 Trials But With Insufficient Evidence for Attribution: Aspartate aminotransferase increased • Decrease in Risk Attribution: 
 • Changed to Less Likely from Likely: Fatigue • Changed to Also Reported on ASTX727 Trials But With Insufficient Evidence for Attribution from Less Likely: Dizziness; Headache • Deleted Risk: 
 • Also Reported on ASTX727 Trials But With Insufficient Evidence for Attribution: Blood bilirubin increased; Colitis; Weight loss • Modified Specific Protocol Exceptions to Expedited Reporting (SPEER) reporting requirements: 
 • Added: Upper respiratory infection; Urinary tract infection • Provided Further Clarification: 
 • Infection is now reported as Lung infection/pneumonia, sepsis, tooth infection, upper respiratory infection, and urinary tract infection.

#	Section	Comments
		
• Footnote #2 previously reported as, “Infection includes all 75 sites of infection under the INFECTIONS AND INFESTATIONS SOC” was deleted.• Footnote #2 is now reported as “The SPEER grade for febrile neutropenia should only be applied to cases of neutropenic fever• associated with hematologic malignancies and NOT for solid tumors.”• Additional changes due to migrating from CAEPR version 2.0 to 2.2
• Replacing Cedazuridine with E7727

NCI Protocol #: 10330

Local Protocol #: 202008172

ClinicalTrials.gov Identifier: NCT04340843

TITLE: A Phase 2 Study of Belinostat and SGI-110 (Guadecitabine) or ASTX727 for the Treatment of Unresectable and Metastatic Conventional Chondrosarcoma

1. OBJECTIVES

1.1 Primary Objectives

- 1.1.1 To conduct a phase 2 clinical trial to evaluate whether combination treatment with belinostat and ASTX727 shows preliminary evidence of clinical activity in unresectable or metastatic conventional chondrosarcoma (CS) using an objective response rate endpoint.

1.2 Secondary Objectives

- 1.2.1 To evaluate the toxicity profile associated with belinostat and ASTX727.
- 1.2.2 To evaluate the progression free survival (PFS) associated with belinostat and ASTX727.
- 1.2.3 To evaluate the toxicity profile, objective response rate and progression free survival among the initial six patients treated with belinostat and SGI-110 (guadecitabine) prior to Amendment 5 in which ASTX727 was substituted for SGI-110 (guadecitabine).

1.3 Correlative Objectives

- 1.3.1 To determine the *IDH1/2* mutational status of subject's tumors and to evaluate for a relationship between presence of *IDH1/2* mutation and clinical benefit from study treatment.
- 1.3.2 To conduct RNAseq analysis using baseline and on-treatment tissue biopsies to study the effects of study treatment on CS gene expression patterns and identify candidate genes which may underlie treatment efficacy.
- 1.3.3 To evaluate for changes in global DNA methylation levels using baseline and on-treatment biopsies and correlate changes in global methylation with clinical benefit from study treatment.
- 1.3.4 To use multiplex immunohistochemistry to interrogate the immune microenvironment in baseline and on-treatment tissue biopsies to define changes in infiltrating immune cell subsets and PD-L1/MHC expression by immune and tumor cells associated with study treatment.

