In a phase 1 study in patients with advanced solid tumors, the maximum tolerated dose (MTD) of belinostat was 1000 mg/m² IV daily, administered over 30 minutes on Days 1-5 of a 21-day cycle (Steele *et al.*, 2008). Dose-limiting toxicities (DLTs) included grade 3 fatigue, diarrhea, and atrial fibrillation, as well as grade 2 nausea/vomiting resulting in inability to complete a full 5-day cycle. A phase 1 study in patients with advanced hematologic neoplasms reported the same MTD (Gimsing *et al.*, 2008). The most common treatment-related adverse events (AEs) (all grades) were nausea (50%), vomiting (31%), fatigue (31%), and flushing (31%). There was one case of grade 3 lymphopenia and two cases of grade 4 renal failure in the context of tumor lysis syndrome (TLS). The only related grade 3 events in more than one patient were fatigue and neurologic symptoms, and no cardiac events were noted. Oral belinostat was studied in 15 patients who were included in the phase 1 trial of IV belinostat in second or subsequent treatment cycles (Steele *et al.*, 2011). High doses, up to 1000 mg/m² orally twice daily for 5 consecutive days, were found tolerable in this small study. In a phase 1 trial of oral belinostat in patients with lymphoma, the drug was found to be safe (no DLTs) at daily doses of 750-1250 mg on Days 1-14 every 3 weeks (Zain *et al.*, 2009). In a phase 2 clinical trial, belinostat was administered IV at 1000 mg/m² daily on Days 1-5 every 21 days in patients with relapsed/refractory AML or newly diagnosed patients with AML over the age of 60 (Kirschbaum *et al.*, 2015). Belinostat was well tolerated; however, only 4 patients displayed stable disease (SD) for at least five cycles. A similar trial of belinostat at the same dose and schedule showed similar activity in myelodysplastic syndrome (MDS), with only one confirmed response (Cashen *et al.*, 2012).

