2.4.2 Exploratory Studies

2.4.2.1 Tumor Immune Microenvironment

The effectiveness of many anti-cancer therapeutics depends upon activity of the immune system. Many cancers alter normal cellular processes to evade immune surveillance, and increasing evidence suggests that immune evasion is accomplished in part through epigenetic modification of genes involved in antigen presentation, expression of immunosuppressive cell surface molecules, suppression of candidate neoantigens, and other mechanisms. There is increasing evidence to support combining epigenetic-based therapies, including HDAC and DNMT inhibitors, with immune checkpoint inhibitors, and clinical trials with these combinations are ongoing (Weisenberger *et al.*, 2006). However, studies evaluating the effects of epigenetic treatments on the immune microenvironment using tissue from prospective clinical trials with HDAC and DNMT inhibitors is limited. We will analyze changes in densities of infiltrating immune cell subsets between pre-treatment and on-treatment specimens to evaluate changes induced by study treatment. We hypothesize that belinostat and SGI-110 (guadecitabine) or ASTX727 treatment will induce expression of MHC and PD-L1 by tumor cells and will increase infiltration of cytotoxic T-cells into chondrosarcoma tumors.

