6.2 General Concomitant Medication and Supportive Care Guidelines

Because there is a potential for interaction of SGI-110 (guadecitabine), ASTX727 and belinostat with other concomitantly administered drugs, the case report form must capture the concurrent use of all other drugs, over-the-counter medications, or alternative therapies. The Principal Investigator should be alerted if the patient is taking any agent known to affect or with the potential for drug interactions. The study team should check a frequently-updated medical reference for a list of drugs to minimize use of or avoid entirely. Appendix D (Patient Clinical Trial Wallet Card) should be provided to patients if available.

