6.2.3 Belinostat

6.2.3.1 Concomitant medications and supportive guidelines

Belinostat is associated with nausea. **Patients must receive prophylactic treatment with a 5-HT3 receptor antagonist for the first two cycles of treatment.** Ondansetron (oral disintegrating tablet 8 mg PO or equivalent) may be administered once prior to each dose of belinostat. Alternatively, granisetron extended-release injection 10 mg SC may be administered once on day one prior to the first administration of belinostat in each treatment cycle. If nausea or vomiting occurs despite the use of a 5-HT3 receptor antagonist, consider the addition of dexamethasone 8-10 mg PO or IV prior to each dose of belinostat. Continuation of the 5-HT3 receptor antagonist after the first two cycles is at the treating investigator's discretion.

As discussed in Section 6.2.1.1 and 6.2.2.1, patients will be administered prophylactic growth factor.

Patients should receive all supportive care appropriate for their medical condition, including, but not limited to, antibiotics, transfusions, and other agents deemed necessary for symptom management, unless specifically prohibited elsewhere in the protocol.

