9.7.4 Changes in Tumor Microenvironment

For quantitative immune multiplexing, data is derived from inForm software, and changes in defined immune cell subsets and expression between baseline and on-treatment samples will be assessed using paired T-tests.

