F	Coagulation factors include: aPTT, INR; required pre-study and as clinically indicated. Local laboratory testing is permitted.													
G	Serum or urine pregnancy test (for women of childbearing potential) must be completed at screening. If results are positive, the patient is ineligible and must be discontinued from the study.													
H	A 12-lead ECG is performed at screening and end of study. Additional ECGs are performed as clinically indicated.													
I	MRI or CT imaging to evaluate disease status is performed at baseline and once every 2 cycles (8 weeks) \pm 5 days. Imaging should be performed prior to the initiation of the next cycle of study treatment whenever possible.													
J	Pre-treatment biopsy is performed within 21 days of C1D1. The pre-treatment biopsy may only be collected after informed consent is obtained. On-study biopsy is performed on Day 3, 4, or 5 of cycle 2, 2-8 hours post-treatment with the study agents whenever possible. If the start of C2 is delayed, the biopsy should be delayed accordingly. The on-study biopsy should not be obtained if the patient has not begun dosing for C2.													
K	Blood collection for germline whole exome sequencing. Pre-treatment collection is performed within 21 days of C1D1. The pre-treatment research blood collection may only be collected after informed consent is obtained.													
L	All screening assessments must be performed within 21 days of C1D1.													
M	All assessments occur on day 1 of the specified week, unless otherwise noted. Start of cycle laboratory assessments may be performed up to 3 days prior to initiating treatment for a new cycle. Between cycle laboratory assessments may be performed \pm 3 days from the scheduled date. Local laboratory testing is permitted.													
N	Off-study evaluations must be performed within 21 days of the last dose of the study drug.													

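### The immune comparison in 9.7.4 makes no allowance for the dexamethasone that some patients may have had in the days before the cycle 2 biopsy

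*Combined protocol and SAP*

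**What the plan says.** - **Reading of the change.** Objective 1.3.4 sets out to "define changes in infiltrating immune cell subsets and PD-L1/MHC expression by immune and tumor cells associated with study treatment". Section 2.4.2.1 is more causal: "We will analyze changes in densities of infiltrating immune cell subsets between pre-treatment and on-treatment specimens to evaluate changes induced by study treatment". Its hypothesis has a direction: treatment will induce MHC and PD-L1 on tumor cells and "will increase infiltration of cytotoxic T-cells into chondrosarcoma tumors".
- **Analysis.** Section 9.7.4 states that "changes in defined immune cell subsets and expression between baseline and on-treatment samples will be assessed using paired T-tests". It has no covariate, stratum, exclusion or sensitivity analysis.
- **Biopsy timing.** Study Calendar, footnote J: "On-study biopsy is performed on Day 3, 4, or 5 of cycle 2, 2-8 hours post-treatment with the study agents whenever possible". The baseline biopsy is taken before treatment, within 21 days of C1D1.
- **Dexamethasone.** Section 6.2.3.1 applies if nausea or vomiting occurs despite the 5-HT3 antagonist that is required in cycles 1 and 2. Investigators should then "consider the addition of dexamethasone 8-10 mg PO or IV prior to each dose of belinostat". Section 7.5 also says to consider it, from grade 1 vomiting upward.
- **Data.** Under section 6.2, "the case report form must capture the concurrent use of all other drugs".
- **Steroid restriction.** The only one in eligibility is in 3.1.9, for patients with treated brain metastases.

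**The concern.** The second biopsy lies inside the five-day belinostat block. A patient who has dexamethasone before each dose of that block will have taken it on every day up to the biopsy. The paired difference in that patient then carries two exposures, the study drugs and a corticosteroid, while the baseline sample usually carries neither.

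Section 9 describes an open-label single-arm trial, so the design cannot separate the two. Only the analysis can, and 9.7.4 does not try, although the data are on the CRF.

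If a corticosteroid lowers lymphocyte density or MHC and PD-L1 expression, it works against the hypothesis in 2.4.2.1. A real increase could be diluted, or a steroid-driven fall reported as an effect of belinostat plus ASTX727. At stake is the reading of an exploratory endpoint for which patients undergo a mandatory research biopsy on treatment.

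**Working it through.** The plan gives no sample size, power, effect size or alpha for the immune endpoint, so there is no figure to reproduce. The check has two parts.

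**1. Exposure at the biopsy.** Belinostat is given on days 1-5. With dexamethasone before each dose from day 1 of cycle 2, a biopsy on day 3, 4 or 5 follows 3, 4 or 5 daily doses. If the 2-8 hour window is kept, the last dose was given earlier the same day.

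**2. Illustration of size.**

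From the documents:
- The ASTX727 cohort is 13-26 patients (9.5), so at most 13 or 26 pairs.
- The test is a paired t-test (9.7.4).
- Nausea and vomiting were 50% and 31% in a phase 1 study of belinostat in hematologic neoplasms (2.2.1.2). Each is listed as likely (>20%) in the belinostat risk list (10.1.1.3).

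Assumed, because the documents do not say:
- The share of pairs exposed, *f*, is 20%, 30% or 50%.
- Dexamethasone shifts the paired difference by *d* = -0.1 to -1.0 SD.
- Alpha is two-sided 0.05, so 2.5% in the lower tail.

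The average bias is *f* × *d*. It runs from 0.20 × (-0.1) = -0.02 SD to 0.50 × (-1.0) = -0.50 SD.

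*No study-drug effect.* Percentage of simulated trials reporting a significant decrease (100,000 replicates, unit SD):

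| Exposed | Shift (SD) | 26 pairs | 13 pairs |
|---|---|---|---|
| 20% | -0.1 | 3 | 3 |
| 20% | -0.5 | 7 | 5 |
| 20% | -1.0 | 14 | 9 |
| 30% | -0.1 | 4 | 3 |
| 30% | -0.25 | 6 | 4 |
| 30% | -0.5 | 11 | 7 |
| 30% | -1.0 | 27 | 14 |
| 50% | -0.1 | 4 | 4 |
| 50% | -0.5 | 22 | 13 |
| 50% | -1.0 | 59 | 32 |

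*True increase of 0.6 SD (assumed).* The expected change is 0.60 + *f* × *d*. At 30% exposed:
- *d* = -0.5: 0.60 - 0.15 = 0.45 SD.
- *d* = -1.0: 0.60 - 0.30 = 0.30 SD.
- Power with 26 pairs falls from 0.84 to 0.58 and 0.27.
- Power with 13 pairs falls from 0.51 to 0.31 and 0.15.

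At the extreme (*f* = 50%, *d* = -1.0) the mean is 0.60 - 0.50 = +0.10 SD.

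*Unexposed pairs only.* At 30% exposed, 0.70 × 26 = 18.2 and 0.70 × 13 = 9.1 pairs remain. Power for 0.6 SD is 0.67 with 18 pairs and 0.35 with 9.

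**The case against.** **Exposure may be low.** Dexamethasone is only to be considered, and only after a mandatory 5-HT3 antagonist has failed. The 50% and 31% are all-grade event rates in another population. They are neither breakthrough rates under this prophylaxis nor rates of dexamethasone use. A reader might infer that many patients will be exposed, but the documents support only that some may be.

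**The steroid effect is not in the documents.** Its direction is general pharmacology and its size is assumed. At -0.1 SD the distortion is trivial, which is why the range starts there.

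**Reversal.** A reader might infer that dexamethasone could turn a real increase into a decrease. With a true change of 0.6 SD, the mean stays positive throughout the range shown, at +0.10 SD in the worst case. Dilution is supported and reversal is not.

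**Dropping exposed pairs.** It is tempting to make the unexposed pairs the main estimate. Dexamethasone use follows nausea or vomiting after treatment starts, so these patients are selected on how they tolerated treatment and may differ in drug effect. This objection stands and shapes the fix.

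**Gene expression.** A reader might carry the figures over to RNAseq. Section 9.7.2 requires an absolute log2 fold change above 2 and an adjusted p below 0.005, so a paired t-test illustration does not transfer.

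**Other co-medication.** G-CSF is required every cycle (6.2.2.1), so every pair has it between the biopsies. Steroid-free pairs still do not isolate the two study drugs. Objective 1.3.4 can be read as covering the regimen with its supportive care, but 2.4.2.1 speaks of induced changes.

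**Conclusion.** The concern holds as an unaddressed route to misattribution in an exploratory analysis. The protocol permits a corticosteroid at the time of the second biopsy, has no control arm, reads the paired change as a treatment effect and plans no use of the exposure data that it collects.

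The size cannot be fixed from the documents. Under the assumed ranges, a false significant decrease occurs in about 3-59% of trials with 26 pairs and 3-32% with 13, against 2.5%. The low end is negligible, and the high end needs both heavy use and a large steroid effect. Twenty-six pairs is itself optimistic: the trial may stop at 13 patients, the assay is listed as optional (5.7), and it uses the third-priority core (5.2).

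No primary, secondary or safety conclusion is affected. The point is worth acting on because prespecification costs little and avoids a post hoc choice of pairs.

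**What to change.** In 9.7.4:

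1. Flag each pair for any systemic corticosteroid in the 7 days before either biopsy, using the concomitant-medication CRF.
2. Keep the all-pairs paired analysis as the main result, and describe it as change on the regimen with its supportive care.
3. Prespecify a sensitivity analysis in unexposed pairs, or regress the paired change on the flag. The intercept is then the change in unexposed pairs.
4. Attribute an immune change to belinostat plus ASTX727 only if the two analyses agree in direction and approximate size. Agreement addresses the steroid only, because G-CSF remains common to all pairs.
5. Report the same flag descriptively for the immune and interferon genes in 9.7.2.

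The cost is one derived variable from data already collected and a few lines of text. The downside is that the sensitivity analysis is small and rests on patients selected by tolerance. It therefore supports the all-pairs result and does not replace it. Antiemetic care is unchanged.
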